- Patients on other antidepressants are allowed to participate only if the antidepressant is prescribed at subtherapeutic doses for a primary indication other than mood disorders. Participants will be made aware in the consent form that the combination of the two antidepressants would be considered investigational and that the safety/efficacy profiles are unknown ²⁸⁻³⁰.
- Current alcohol or substance use disorder.
- Inability to provide consent.
- Current alcohol and/or substance use disorder as confirmed by the M.I.N.I 7.0.2.
- Presence of comorbid psychiatric disorder that is a primary focus of clinical concern as confirmed by the M.I.N.I. 7.0.2.
- Medications approved and/or employed off-label for cognitive dysfunction (e.g., psychostimulants).

- Any medication for a general medical disorder that, in the opinion of the investigator, may affect cognitive function.
- Use of benzodiazepines within 12 hours of cognitive assessments.
- Consumption of alcohol within 8 hours of cognitive assessments.
- Physical, cognitive, or language impairments sufficient to adversely affect data derived from cognitive assessments.
- Diagnosed reading disability or dyslexia.
- Clinically significant learning disorder by history.
- Electroconvulsive therapy (ECT) in the last 6 months.
- History of moderate or severe head trauma (e.g., loss of consciousness for >1 hour), other neurological disorders, or unstable systemic medical diseases that in the opinion of the investigator are likely to affect the central nervous system.
- Pregnant and/or breastfeeding.
- Received investigational agents as part of a separate study within 30 days of the screening visit.
- Actively suicidal/presence of suicidal ideation or evaluated as being at suicide risk (as per clinical judgment).
- Currently receiving treatment with Monoamine Oxidase Inhibitors (MAOIs) antidepressants, antibiotics such as linezolid, or intravenous methylene blue.
- Previous hypersensitivity reaction to vortioxetine or any components of the formulation. Angioedema has been reported in patients treated with vortioxetine.
- Serotonin syndrome.
- Abnormal bleeding.
- Previous history of mania/hypomania.
- Angle closure glaucoma.
- Hyponatremia.
- Moderate hepatic impairment.
- Active seizure disorder/epilepsy, not controlled by medication (per study physician assessment).
- Presence of any unstable medical conditions.

Recruitment

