Recruitment will take place via media announcements (e.g., print, social media, public broadcasting stations). Announcement of study recruitment will also be provided to primary health care providers in Canada.

Study Visits

Study visits may be conducted remotely (e.g. zoom), by telephone or in-person. Visits with the study physician will primarily occur via a secure online platform (e.g. OTN) or by telephone. If required/requested, in-person visits with the study physician may be scheduled.

Participants may be emailed a secure, unique and anonymized RedCap link to complete self-report questions at home within 24 hours of their scheduled visit (before or after visit). This is to reduce participant burden during the visit with research staff/study physicians. Participants will

be asked to complete self-report questionnaires at the same time block of the day during all study visits (i.e. all mornings, afternoons or evenings).

Pre-Screen

Participants will be pre-screened via telephone, email, or an online form to determine if they meet above noted inclusion and exclusion criteria.

Screening Visit (Visit 0)

Once participants provide written, informed consent, they will undergo a comprehensive assessment to determine eligibility during the screening visit. Details of assessments completed are included in Table 1.

Baseline (Visit 1)

Participants will undergo the various assessments listed in Table 1. In addition, participants will have their blood drawn and may be invited to participate in an optional fMRI scan (see details below). Participants will also be assessed by a study physician at one time point between the screening and baseline visits and be provided a prescription for vortioxetine. Research staff (i.e. research coordinators/research assistants) will dispense the medication to the participant based on the direction from the study physician/prescription from the study physician for the first two weeks of the study. For remote participants, research staff will mail medication for the first two weeks of the study with appropriate temperature monitoring.

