Laboratory Assessment: Participants will be asked to fast for 8 hours prior to their baseline (visit 1) and week 8 (visit 4). Participants will have blood drawn for standard clinical parameters. These include glucose, insulin, electrolytes, liver and kidney function tests, lipids, CBC, inflammatory markers (e.g. CRP, ESR), albumin and protein. Participants may also have their blood drawn for various exploratory secondary analyses (e.g. cytokines). Approximately 20 mL of blood will be drawn in 4-5 blood tubes. Two of these tubes will include lavender tubes with EDTA for exploratory analyses. A urine or blood pregnancy test will be conducted for all female participants.

Remote participants will be provided a blood requisition form via email or mail to have clinical blood drawn and analyzed at the participant's local blood lab facility. Blood will not be collected for exploratory purposes from remote participants. Female participants may provide a blood or urine sample to the local blood lab to confirm non-pregnancy. Participants may also be mailed a home pregnancy test.

Exploratory Blood Analyses: For participants seen in-person, they will be able to volunteer to provide a blood sample for exploratory analyses. The sample will be collected at a local blood lab (e.g. Mount Sinai Hospital), followed by processing and storage of the sample at the Biospecimen Repository and Processing Lab (Lunenfeld-Tanenbaum Research Institute, Sinai Health). Participants may also have blood drawn at the same time for clinical purposes at Mount Sinai Hospital. The clinical blood tubes will be delivered to another local lab (e.g. Dynacare, LifeLabs) for analyses. Alternatively, participants may also have blood drawn separately for clinical analyses at a local blood lab near them - this will result in two separate blood draws.

fMRI: A subset of participants may be offered the opportunity to have an fMRI scan completed at baseline and endpoint for secondary, exploratory purposes. This is optional and not the primary focus of the study. Participants may still participate in the study and decide not to participate in this component. During the imaging, participants will be asked to complete a cognitive task (e.g. Effort Expenditure for Rewards Task, Trails Making Test A/B). Participants will be awarded the amount of money they earn during this task, on top of the standard compensation to all participants. Please see “Participant Compensation” for more details.

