Abbreviations: ^a: BAS: Behavioural Activation Scale; DSST: Digit Symbol Substitution Test; EQ-5D-5L: 5-Level EQ-5D version; fMRI: functional magnetic resonance imaging; FSS: Fatigue Severity Scale; GAD-7: Generalized Anxiety Disorder, 7-item; IPAQ: International Physical Activity Questionnaire; EEfRT: Effort Expenditure for Rewards Task ; M.I.N.I: Mini-International Neuropsychiatric Interview; MoCA: Montreal Cognitive Assessment; PCFS: Post-Covid Functional Scale; PDQ-20: Perceived Deficits Questionnaire, 20-item; Quick Inventory of Depressive Symptomatology (16-Item) (Self-Report) (QIDS-SR16); RAVLT: Rey's auditory verbal learning test; RPE: Borg Rating of Perceived Exertion Scale; SDS: Sheehan Disability Scale; SETS: Stanford Expectations of Treatment Scale; SHAPS: Snaith-Hamilton Pleasure Scale; TMT-A/B: Trails Making Test-A/B; WHO-5: World Health Organization Well-Being Index, 5-item.

*One physician assessment will be conducted between the baseline and screening visit.

**May be conducted remotely.

Sample Size

- Total recruitment N=200 (i.e., 100 subjects allocated to vortioxetine [5-20 mg] and placebo each).
- The target sample size is based on effect sizes reported by previous clinical trials that evaluated the efficacy of antidepressants vs placebo and nutraceuticals in individuals with chronic fatigue syndrome ^{6,23-25}.
- The effect size of vortioxetine on DSST-measured cognitive function is estimated at approximately 0.2-0.5 ^{26,27}. Previous experience without patients enrolled in clinical trials (investigator-initiated trials) with vortioxetine as part of the THINC-it tool validation indicated that vortioxetine improves measures of processing speed (the prominent domain validated by the DSST) of significance with a sample size of 200.
- It is then estimated that a sample size of 100 per treatment arm would detect clinically relevant change with vortioxetine treatment on DSST as the dependent measure ^{27,31}.

Feasibility

- It is estimated, based on prior general population research conducted by the BCDF, that recruitment will take approximately 12 months.
- Community research ethics board approval, 2-4 weeks (BCDF is an independent research center not requiring university- or hospital-based REB reviews).

Description of Study Procedures

Efficacy Assessments

Digit Symbol Substitution Test (DSST)

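### The first two weeks of study drug can be released before anyone has reviewed the baseline sodium, liver and pregnancy results, although each bears on an exclusion

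*Combined protocol and SAP*

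**What the plan says.** The Exclusion Criteria list hyponatremia, "Moderate hepatic impairment" and "Pregnant and/or breastfeeding", with no cut-off or required test for any of them.

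Under Screening Visit (Visit 0), once participants have consented, "they will undergo a comprehensive assessment to determine eligibility during the screening visit". Table 1 marks the inclusion/exclusion check in the screening column only.

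Under Baseline (Visit 1), participants will "be assessed by a study physician at one time point between the screening and baseline visits and be provided a prescription for vortioxetine". The Table 1 footnote agrees: "One physician assessment will be conducted between the baseline and screening visit". The table marks no physician assessment in the baseline column.

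Laboratory assessments are marked at baseline and week 8 only. The Laboratory Assessment text says of the standard clinical parameters: "These include glucose, insulin, electrolytes, liver and kidney function tests". It also provides a urine or blood pregnancy test for every female participant. Remote participants take a requisition to a local laboratory.

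On release of the first supply, research staff will "dispense the medication to the participant based on the direction from the study physician/prescription from the study physician for the first two weeks". For remote participants, "research staff will mail medication for the first two weeks of the study". Neither sentence mentions a laboratory result.

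**The concern.** The three exclusions are ones that a blood or urine test can reveal in a person with no known history, and the protocol already orders those tests. It places them after eligibility has been determined and after the only scheduled physician contact before dosing. It then lets non-physician staff release drug on a prescription that may already exist. Followed as written, the schedule allows a participant with an undiagnosed excluded condition to start vortioxetine while the result that would have excluded them is outstanding or unread. The Side effects section names hyponatremia as a risk of the drug. What is at stake is participant safety.

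**Working it through.** The plan states no figure to reproduce, so the check is mainly one of sequence.

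**Order of events**

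1. Screening, 1 to 21 days before baseline (Table 1): eligibility determined; no laboratory test.
2. Between screening and baseline (Baseline section, Table 1 footnote): the one pre-dose physician assessment, and the prescription.
3. Baseline (Table 1, Laboratory Assessment): first scheduled electrolytes, liver function and pregnancy test.
4. First supply (Baseline section): dispensed or mailed on prescription or physician direction. For remote participants, neither the blood draw nor the mailing is dated relative to the first dose.
5. Week 2, 14 ± 2 days, so day 12 to 16: next scheduled physician assessment. Its stated purpose is to decide on a dose increase; review of baseline laboratory results is not named.

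The prescription can therefore precede the baseline draw by up to about 21 days.

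**Is there a hold elsewhere?**

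- Clinical Laboratory Tests: an unexplained clinically significant abnormality is repeated and followed up. A urine pregnancy test is done if there was no hCG screen.
- Premature Discontinuation: laboratory events or failure to meet entry criteria can be grounds for stopping.
- Clinical Laboratory Changes: values new or worse than baseline are recorded if they meet stated criteria, and potential Hy's Law cases are reported promptly.
- Laboratory Assessment and Remote Visits: remote female participants give a sample, or may be mailed a home test, to confirm that they are not pregnant.

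The abnormal-value and discontinuation rules act only once a result is known. The pregnancy provisions do not require a documented negative before release.

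**A related mismatch.** Laboratory Assessment includes liver function tests. The list under Clinical Laboratory Tests names sodium but no liver enzymes or bilirubin.

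**Exposure per affected participant** (starting doses from Study Medication: Vortioxetine)

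- First supply: 14 × 10 mg = 140 mg, or 14 × 5 mg = 70 mg.
- If the result is acted on after 1, 3 or 7 days (assumed; no turnaround is given): 10, 30 or 70 mg at 10 mg/day; 5, 15 or 35 mg at 5 mg/day.

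**Number affected.** Only the vortioxetine arm, 100 of 200 (Sample Size), can be exposed to drug. Let p be the prevalence of an undiagnosed excluding sodium or liver result, and c the share caught before the first dose. Expected number = 100 × p × (1 − c). Both inputs are assumptions:

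| p | c = 0 | c = 0.5 | c = 0.9 |
|---|---|---|---|
| 0.1% | 0.10 | 0.05 | 0.01 |
| 0.5% | 0.50 | 0.25 | 0.05 |
| 1% | 1.00 | 0.50 | 0.10 |

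Pregnancy is not in this count; the documents give nothing from which to estimate it.

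**The case against.** The best reply is that the protocol is silent here rather than wrong. Release depends on physician direction or prescription, so a physician can hold it, and a site procedure could supply the missing step. The exclusions sit in a list of clinical conditions without cut-offs, checked by pre-screen, history, medication review and physician assessment. The bloods are classed as safety assessments. On that view, using them to decide eligibility is a preference and the plan does not contradict itself.

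Much of this stands. History and the physician assessment can catch known cases, so only undiagnosed or new ones remain. The pregnancy element is softer, since a urine or home test is quick and the stated aim for remote participants is to rule pregnancy out. The prevalence, capture and turnaround figures are all assumed.

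It does not close the gap. Permission to wait is not a requirement to wait, and an existing prescription is enough for staff to release drug. Nor can results be assumed to be at hand for in-person participants, because clinical tubes go to another laboratory or are drawn separately near the participant's home.

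A reader might infer that the protocol orders dosing before results. It does not: the order is left open, both in person and remotely. A reader might also take 14 doses as the most anyone could receive before the result is read. That does not follow, because week 2 carries no stated review of the baseline results either.

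**Conclusion.** The point holds as a sequencing gap in participant safety, of low to moderate severity. The documents do not require the baseline sodium, liver or pregnancy results to be reviewed before first release, and every safeguard for an abnormal result acts after it is known. The number affected is unknown and probably small: at most about one vortioxetine participant with an excluding sodium or liver result under the assumptions above. Per affected person, the first supply is 140 mg or 70 mg, and exposure could continue beyond it.

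It would be going too far to say that the efficacy result is compromised. Nothing here alters the DSST analysis, the sample size or the error rate, and the primary comparison is not affected.

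**What to change.** Amend Baseline (Visit 1) and Table 1 so that the first supply is neither dispensed nor mailed until:

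- the study physician has documented review of the baseline sodium and liver results against the exclusions, using clinical judgment because no cut-offs are set; and
- a negative pregnancy test is documented for female participants, as applicable.

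Draw the clinical bloods within the screening window, a few days before Visit 1, and move the 8-hour fast to the draw. The baseline DSST then stays next to the first dose. Where screening is only one day before baseline, release waits for the result. Add the liver tests in Laboratory Assessment to the Clinical Laboratory Tests list so that the two agree. No test is needed beyond those already named in Laboratory Assessment.

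The cost is a few days' delay or a separate laboratory trip for some participants; Laboratory Assessment already allows separate draws. If release has to wait until after Visit 1, a short interval opens between the baseline DSST and the first dose in both arms, and week 8 should then be counted from the first dose.

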Cognitive Test: CogState DSST – Symbols - “In this test, subjects are presented with a legend that defines nine symbols, with each symbol corresponding to a digit from 1 to 9. The subject is then presented with a conveyor belt in the middle of the screen that displays a series of empty boxes labelled with a number. The subject must select the symbol that corresponds to the number of a given highlighted box from symbol options presented at the bottom of the screen. The subject must try to place as many correct symbols in the boxes as possible over the duration of the test.”³⁶

Time: 3 min

Domain: Attention

2. Operation: Choice Reaction Time

Cognitive Test: CogState Detection Test - "The Detection test measures processing speed using a simple reaction time paradigm. The on-screen instructions ask: "Has the card turned over?". A playing card is presented face down in the center of the screen. The card flips over so it is face up. As soon as the card flips over the participant must press "Yes". The participant is encouraged to work as quickly as they can and be as accurate as possible." ³⁶

Time: 3 min

3. Operation: Choice Reaction Time

Cognitive Test: CogState Identification Test - "The Identification test measures attention using a choice reaction time paradigm. The on-screen instructions ask: "Is the card red?". A playing card is presented face down in the center of the screen. The card flips over so it is face up. As soon as it flips over the participant must decide whether the card is red or not. If it is red the participant should press "Yes", and if it is not red the participant should press "No". The participant is encouraged to work as quickly as they can and be as accurate as possible." ³⁶

Time: 3 min

Domain: Memory

4. Operation: Visual Learning

Cognitive Test: CogState One Card Learning Test - "The One Card Learning test measures visual memory using a pattern separation paradigm. The on-screen instructions ask: "Have you seen this card before in this test?". A playing card is presented face up in the center of the screen and the participant must decide whether they have seen the card before in this test. The participant is encouraged to work as quickly as they can and be as accurate as possible." ³⁶

Time: 6 min

Each participant will be completing the battery twice on the same day to assess test reliability and as an objective measure of fatigue. The CogState Online Cognitive Battery will be administered at baseline (visit 1), and weeks 2 and 8 visits.

Quick Inventory of Depressive Symptomatology, Self-Report (QIDS-SR-16)

The QIDS-SR-16 ³⁷ is a 16-item self-rated scale designed to assess the severity of depressive symptoms in the nine diagnostic symptom domains of a major depressive episode, exclusive of atypical or melancholic symptoms, over the past 7 days. The QIDS-SR-16 is sensitive to change with various treatments, demonstrating its utility in research settings. The total score ranges from 0 to 27 with 0 representing no depression and 27 representing severe depression. The total score is the sum of the 9 symptom domains. The QIDS-SR-16 will be administered at baseline, and weeks 2, 4, and 8 visits.

Patient Health Questionnaire, 9-item (PHQ-9)

The PHQ-9 is a self-rated measure of depressive symptom severity in the past two weeks. Each of the nine items is rated on a Likert scale, ranging from 0 (not at all) to 3 (nearly every day), and summed for a total score between 0 (no symptoms) to 27 (most severe) ³⁸. The standardized cut-off scores are ≥5, 10, 15, and 20 for mild, moderate, moderate-severe, and severe symptoms, respectively. The PHQ-9 will be administered at baseline, and weeks 2, 4, and 8 visits.

Perceived Deficits Questionnaire, 20-item (PDQ-20)

The PDQ-20 is a self-report measure originally developed for the assessment of cognitive impairment in the past two weeks for multiple sclerosis ³⁹. It is a 20-item questionnaire that generates 4 subscale scores (attention/concentration, retrospective memory, prospective memory, and planning/organization), and a total score which is the sum of the scores for the 20 items. Each item is rated on a 5-point scale ranging from 0 (never) to 5 (almost always). The combined subscales yield a total score ranging from 0 to 80, with a higher score indicating greater perceived cognitive impairment. The PDQ-20 will be administered at baseline, and weeks 2, 4, and 8 visits.

Snaith-Hamilton Pleasure Scale (SHAPS)

The SHAPS is a self-report measure designed to assess the degree to which a person is able to experience pleasure or the anticipation of a pleasurable experience ⁴⁰. It includes 14 items involving four domains of hedonic experience: interest/pastimes, social interaction, sensory experience, and food/drink. Each item has four possible responses: strongly disagree, disagree, agree, or strongly agree. For each item, a score of 2 or less constitutes a “normal” score, while an “abnormal” score is defined as 3 or more, and the final score ranges from 0 to 14 ⁴¹. The SHAPS will be administered at baseline, and weeks 2, 4, and 8 visits.

Generalized Anxiety Disorder Scale, 7-item (GAD-7)

The GAD-7 is useful in primary care and mental health settings as a screening tool and symptom severity measure for the seven most common anxiety disorders ⁴². Participants choose one of 4 severity scores (i.e., 0: not at all, 1: several days, 2: more than half the days, 3: nearly every day) associated with problems related to the common anxiety disorders and then indicate the degree to which these problems caused functional and/or social difficulties over the past two weeks. Scores are determined by calculating the values for each column. The minimum score is 0 and the maximum score is 32, where higher scores indicate worse anxiety. The GAD-7 will be administered at baseline, and weeks 2, 4, and 8 visits.

EQ-5D, 5-level (EQ-5D-5L)

The EQ-5D is a standardized measure of health status for clinical and economic appraisal that was developed by the EuroQol Group. The 5-level version of the EQ-5D (i.e., EQ-5D-5L) consists of a descriptive system and a visual analogue scale and has been validated in 34 countries, including Canada ^{43,44}. The descriptive system comprises five dimensions: mobility, self-care, usual activities, pain/discomfort and anxiety/depression. Each dimension has five

response levels: no problems, slight problems, moderate problems, severe problems, unable to/extreme problems, and the participant is asked to rate their present health (i.e., “your health today”). Responses are coded as single-digit numbers expressing the severity level selected in each dimension, ranging from 1 (no problems) to 5 (extreme problems). A participant’s self-rated health is recorded on a vertical visual analogue scale (range 100 to 0), where the endpoints are labelled ‘The best health you can imagine’ (100) and ‘The worst health you can imagine’ (0). EQ-5D-5L health states can be summarized to derive how good or bad a health state is according to the preferences of the general population of a country/region. The EQ-5D-5L will be administered at baseline, and weeks 2, 4, and 8 visits.

World Health Organization Well-Being Index, 5-item (WHO-5)

The WHO-5 is a measure of overall well-being, rated on a scale of 0 to 25, with higher scores denoting higher quality of life in the past two weeks ⁴⁵. There are five items, each rated on a five-point Likert scale (5-All the time to 0-At no time). A score below 13 denotes poor wellbeing. A $\geq 10\%$ difference denotes a significant change. The WHO-5 will be administered at baseline, and weeks 2, 4, and 8 visits.

Fatigue Severity Scale (FSS)

The Fatigue Severity Scale (FSS) is a self-rated 9-item measure used to evaluate the impact of fatigue within the last week ⁴⁶. Responses to the FSS are based on the past week and each statement may be rated from a scale of 1 to 7 where 1 represents “disagree” and 7 represents “agree”. The minimum score that can be achieved from this scale is 9, and the maximum is 63. A total score of 36 or more suggests the presence of fatigue. The FSS will be administered at baseline, and weeks 2, 4, and 8 visits.

Behaviour Inhibition System/Behavioural Activation System (BIS/BAS)

The behaviour inhibition system (BIS)/ behavioural activation system (BAS) is a 24-item self-report questionnaire ⁴⁷. This questionnaire assesses aversion to threat as well as reward-seeking behaviour. Items are based on a 4-point Likert scale ranging from 1 (i.e., very true for me) to 4 (very false for me). Items 1, 6, 10, 13, 15, 18 and 20 represent BIS (i.e., punishment sensitivity scale). Items 3, 5, 11, 14 and 19 represent the BAS Reward Responsiveness. Items 2, 7, 9 and 17 represent BAS drive (i.e., motivation and pursuit to achieve goals). Items 4, 8, 12 and 16 represent BAS Fun Seeking (i.e., to seek new reward as well as obtain it spontaneously). BIS/BAS scores may be calculated based on the sum of each subsection. The BIS/BAS will be administered at baseline, and weeks 2, 4, and 8 visits.

International Physical Activity Questionnaire (IPAQ)

The International Physical Activity Questionnaire (IPAQ) is a 7-item scale that measures various intensities of physical activity as well as sitting time based on the past 7 days ⁴⁸. The minimum number of days is 0 and the maximum number of days is 7. The IPAQ is administered by research staff at baseline, week 4 and week 8 visits.

Post-COVID-19 Functional Status Scale (PCFS)

The Post-COVID-19 Functional Status (PCFS) scale assesses present functional ability (i.e., “in your current daily life”) as it relates to daily activities (including work and/or school) ⁴⁹. The PCFS is based on a grading system wherein the lowest grade 0 indicates no limitations/symptoms and the highest grade 4 represents the most limitations. The PCFS will be administered at baseline, and weeks 2, 4, and 8 visits.

Effort-Expenditure for Rewards Task (EEfRT)

The Effort-Expenditure for Rewards Task (EEfRT) is a multi-trial task that measures reward and motivation ⁵⁰. Participants are given an opportunity to earn a monetary reward based on successful completion of a task under various reward probabilities. In each trial, participants may choose to complete either the “easy task” or “hard task”. To complete the “easy task”, the participant must use their dominant index finger and press the space bar 30 times within 7 seconds. To complete the “hard task”, the participant must use their non-dominant little fingers and press the bar 100 times within 21 seconds. The value associated with the “easy task” is \$1 while the value associated with the “hard task” may vary from \$1.24-\$4.30. However, successful completion of the task does not guarantee delivery of the monetary reward. More specifically, a probability is applied to the each trial and the probability varies from trial to trial. . This probability and the monetary value associated with a particular trial’s “easy” and “hard” tasks is presented to the participant so they may make an informed decision as to which task they would like to complete. The EEfRT will be administered at baseline and week 8 visit. Participants are notified before they start the EEfRT task that they will be awarded the entire monetary value they earn from completing this task.

fMRI

Individuals who participate in the fMRI will complete a cognitive task (e.g., EEfRT, TMT A/B) to obtain various functional, physiological and anatomical measurements. This is a secondary measure in this study and the data will be used for various exploratory analyses. Analyses may include standard anatomical examination, magnetic resonance spectroscopy (MRS) to measure brain chemistry; diffusion tensor imaging (DTI) to measure the electrical connections between neurons and arterial spin labelling (ASL) to measure blood flow in the small vessels of the brain.

Exploratory Blood Analyses

Plasma samples will be collected and stored for exploratory analyses. Please see above “Baseline (Visit 1)” for further description of the procedure.

Safety Assessments

Clinical Laboratory Tests

Blood samples will be obtained at baseline for routine laboratory test:

- Haematology: complete blood count (CBC)
- Biochemistry: hemoglobin A1c (HbA1C), Sodium, Potassium, Lipid Assessment (includes cholesterol, HDL-C, Triglycerides, calculated LDL-C & Chol/HDL-C ratio)
- Other tests: Chloride, Bicarbonate, C-reactive peptide (CRP), erythrocyte sedimentation rate (ESR), estimated glomerular filtration rate (eGFR)

- hCG pregnancy screen (as applicable)

A urine pregnancy test will be administered if no hCG pregnancy screen has been conducted.

In the event of an unexplained clinically significant abnormal laboratory test value, the test should be repeated and will be followed up until it has returned to the normal range and/or an adequate explanation of the abnormality is found.

Adverse Events

All AEs occurring after the participant signs the ICF and up to the last study event will be recorded. Any unresolved AEs that are ongoing at the end of the study will be followed until resolution or no longer considered clinically significant by the investigator.

Other Assessment Instruments

Mini International Neuropsychiatric Interview Version 7.0.2 (M.I.N.I. Version 7.0.2)

The MINI was designed as a brief structured interview for the major Axis I psychiatric disorders in DSM-5 and International Classification of Diseases-10. Validation and reliability studies have been done comparing the MINI to the Structured Clinical Interview for DSM-5 Patient Edition and the Composite International Diagnostic Interview (a structured interview developed by the World Health Organization). Version 7.0.2 of the MINI will be used for this study. The results of these studies show that the MINI has similar reliability and validity properties, but can be administered in a much shorter period (mean 18.7 ± 11.6 min, median 15 min) than the above referenced instruments. It can be used by clinicians after a brief training session. At screening, participants will be assessed for MDD and BD, as documented by DSM-5 criteria, and the lack of other psychiatric diagnoses will be confirmed by use of the MINI.

Montreal Cognitive Assessment (MoCA)

The MoCA is a 10-minute cognitive screening tool designed to detect mild cognitive impairment⁵¹. The MoCA evaluates short-term memory recall, visuospatial abilities, executive functioning, attention, concentration, and working memory, language, and orientation to time and place. It is a one-page 30-point test. In clinical practice, patients screened and found to have a MoCA score over 26 would be extremely unlikely to meet clinical and neuropsychological criteria for MCI even after extensive evaluation. The MoCA demonstrates high test-retest reliability, and good internal consistency, and there is a close correlation between MoCA and MMSE scores. Version November 7, 2004 will be administered by clinicians who have completed the official MoCA training and certification (<https://www.mocatest.org/training-certification/>). At baseline in-person visits, participants will be assessed for mild cognitive impairment (operationalized as a MoCA score <26).

Stanford Expectations of Treatment Scale (SETS)

The SETS is a self-report tool designed to measure patient outcome expectancy in clinical trials⁵². The six-item SETS contains two subscales: positive expectancy ($\alpha = 0.81-0.88$) and negative expectancy ($\alpha = 0.81-0.86$). Each of the six items includes 7 selection options: strongly disagree, moderately disagree, slightly disagree, neither agree nor disagree, slightly

agree, moderately agree, strongly agree. The positive and negative subscales demonstrate strong internal reliability and are able to predict post treatment response. Most participants are able to complete the SETS in approximately 1 min. The SETS will be administered at baseline visits.

Study Site

The study will be conducted at the Brain and Cognition Foundation (BCDF) main site in Toronto ([name]). BCDF is a non-profit organization engaged in research and educational activities as it relates to brain health and disease, including but not limited to studies in persons with mood disorders, as well as persons who are at-risk for mood disorders. BCDF conducts both proof-of-mechanism, as well as phase 1-3 clinical trials and is one of the most active clinical research organizations in the world based on bibliometrics. Study medication and placebo will be stored in a secured/locked cabinet and office at BCDF and medication will be dispensed by research staff per instruction/prescription of the study physician.

The study physician will be based out of the medical clinic at CRTCE/KJK HealthPlex in Mississauga. As part of participants' ongoing clinical monitoring and care, all participants will have a medical file opened for them at CRTCE/KJK HealthPlex. The study physician evaluating the participant will be documenting the visits in the participant's medical chart at CRTCE/KJK HealthPlex. The majority of the study visits with the study physician will be conducted remotely. However, in-person visits with the study physician may be scheduled at CRTCE/KJK HealthPlex upon the request of the participant or the study physician.

Participants will complete blood draws for clinical and exploratory blood analyses at a local laboratory near the BCDF office in Toronto. Exploratory blood samples will be stored at the Biospecimen Repository and Processing Lab (Lunenfeld-Tanenbaum Research Institute, Sinai Health). Please see "Baseline (Visit 1)" for more details.

fMRI scans are completed at an external institution (e.g. Sunnybrook Health Sciences Centre, University of Toronto). The research staff will inform participants where these scans will be taking place.

Remote Visits

Due to the ongoing COVID-19 pandemic, participants may choose to participate in the study completely remotely. Study visits will be conducted over online (e.g. Zoom) and telephone platforms. Visits with the study physician may be done over the secure Ontario TeleNetwork (OTN) or telephone. Participants will be mailed the study medication. Anthropometrics (e.g. height and weight) will be self-reported by participants. Participants will be mailed or emailed a lab requisition form to complete standard clinical blood tests at their local blood lab. Female participants will be asked to provide a urine or blood sample to confirm non-pregnancy. Female participants may also be mailed a home pregnancy test.

Study Flow

Study Flow

Vortioxetine Dose

18-64 years: Start at 10mg once daily (OD) for the first two weeks, then dosed up 20mg OD thereafter.

65 and above years: Administered 5mg OD for the first two weeks, then dosed up 10mg OD thereafter.

Primary Outcome

[figure not shown]
Digital Symbol Substitution Test (DSST) and CogState Online Cognitive Battery assessed at weeks 0, 2 and 8.

Secondary Outcome

fMRI and Effort-Expenditure for Rewards Task (EEfERT) assessed at weeks 0 and 8.

Trails Making Test-A and B (TMT-A/B) and Rey's Auditory Verbal Learning Test (RAVLT) assessed at weeks 0, 2 and 8.

Perceived Deficits Questionnaire-20 (PDQ-20), Generalized Anxiety Disorder-7 (GAD-7), Snaith-Hamilton Pleasure Scale (SHAPS), Fatigue Severity Scale (FSS), Post-Covid Functional Scale (PCFS), World Health Organization-5 (WHO-5), Sheehan Disability Scale (SDS), Behavioural Activation Scale (BAS), 5-Level EQ-5D version (EQ-5D-5L), Quick Inventory of Depressive Symptoms (16-Item) (Self-Report) (QIDS-SR16) and International Physical Activity Questionnaire (IPAQ) assessed at weeks 0, 2, 4 and 8.

Conditions for Withdrawal From the Study

Premature Discontinuation

If participation in the study is terminated prematurely for any reason, the reason for such early termination should be documented. The reason for any early termination should be recorded, providing as much information as possible.

The reason for early termination can be selected from as follows:

- Screen Failure: Participant does not qualify to participate in the study.
- Lack of efficacy (e.g., increased suicidality).
- Adverse Event: Clinical or laboratory events occurred that, in the medical judgment of the investigator for the best interest of the participant, are grounds for discontinuation. This includes serious and non-serious AEs regardless of relation to study medication.
- Death: The participant died.
- Withdrawal of Consent: The participant desired to withdraw from further participation in the study in the absence of an investigator-determined medical need to withdraw. If the participant gave a reason for withdrawing, it should be recorded in the eCRF.
- Protocol Violation: The participant's findings or conduct failed to meet the protocol entry criteria or failed to adhere to the protocol requirements (e.g., drug non-compliance, failure to return for a defined number of visits, becoming pregnant during trial). The violation necessitated early discontinuation from the study.
- Lost to Follow-Up: The participant stopped coming for visits and study personnel were unable to contact the participant.

- Non-compliance: The participant was non-compliant with study visits or procedures.
- Other: The participant was discontinued for a reason other than those listed above.

Withdrawal Procedures and Next Steps

